12.7. Analyses of Secondary Endpoints

The primary analyses for the secondary endpoints will be conducted using all available data in the mITT population, however, various sensitivity analyses will be presented as detailed below.

All analyses for the secondary effectiveness endpoints will be presented for the mITT and PP analysis populations, while mITT analysis population only will be used for safety endpoints. No imputation for missing data for the secondary endpoints is planned.

12.7.1. Secondary Safety Analyses

Main Analysis

The number and proportion of subjects experiencing any device- and/or procedure-related adverse event will be tabulated for each group. Non-inferiority at 36 months will be calculated using a normal approximation test (Z-test) for a difference in binomial proportion. Non-inferiority will be achieved if the lower limit of the 95% confidence interval for the difference in proportions (Comparator – Altis) is greater than -0.15 in the ITT analysis population. If non-inferiority is achieved and the lower limit of the 95% confidence interval for difference in proportions (Comparator – Altis) is greater than 0, superiority of Altis can also be claimed. As this follows a simple closed test procedure, no multiplicity adjustment is necessary.

The primary analysis of this endpoint will include all available data from the mITT analysis population. Subjects that have not experienced a device- and/or procedure-related event and who have missing data at 36 months will be assumed to be free of such an adverse event.

Sensitivity Analyses

The potential impact on the endpoint inference of all subjects with missing endpoint data will be assessed via various sensitivity analyses that include best case, worst case and tipping point analysis. In addition, a Kaplan-Meier product limit analysis that right censors subjects lost to follow-up will be conducted to further understand the potential impact of subject loss. All sensitivity analyses will be based on the mITT analysis set.

12.7.2. Revision/Resurgery Analyses

Main Analysis

The number and proportion of subjects experiencing any revision/resurgery will be tabulated for each group. Non-inferiority at 36 months will be calculated using a normal approximation test (Z-test) for a difference in binomial proportion. Non-inferiority will be achieved if the lower limit of the 95% confidence interval for the difference in proportions (Comparator – Altis) is greater than -0.10 in the mITT analysis population. If non-inferiority is achieved and the lower limit of the 95% confidence interval for difference in proportions (Comparator – Altis) is greater than 0, superiority of Altis can also be claimed. As this follows a simple closed test procedure, no multiplicity adjustment is necessary.

The primary analysis of this endpoint will include all available data from the mITT analysis population. Subjects that have not experienced a revision/resurgery and who have missing data at 36 months will be assumed to be free of such an event.

Sensitivity Analyses

The potential impact on the endpoint inference of all subjects with missing endpoint data will be assessed via various sensitivity analyses that include best case, worst case and tipping point analysis. In addition, a Kaplan-Meier product limit analysis that right censors subjects lost to follow-up will be conducted to further understand the potential impact of subject loss. All sensitivity analyses will be based on the mITT analysis set.

12.7.3. 24-Hour Pad Weight

There are both continuous and categorical measures evaluated in association with the 24-hour pad weight. Differences in 24-hour Pad Weight will be assessed at 6, 12, 18, 24, and 36 months. Summary statistics for 24-Hour pad weight and change from baseline will be summarized by group and visit. The change from baseline in 24-hour pad weight will be tested separately at each specific timepoint for superiority of the Altis group compared to the Comparator group, and will be based on the mITT analysis population. As 24-hour pad weight and change from baseline in 24-hour pad weight are not study endpoints, only available data will be included with no imputation for missing data.

Additionally, change from baseline in 24-hour pad weight in the Altis group will be compared to the Comparator group using a linear mixed model with repeated effects to understand the effect of pad weight changes over time. An unstructured correlation matrix will be specified to allow for maximal flexibility, but if convergence is not achieved, an autocorrelated or compound symmetry matrix will be used instead. An interaction term for time and treatment will also be assessed in the mixed model.

The secondary effectiveness endpoint of proportions of subjects with $\geq 50\%$ reduction in pad weight from baseline will be summarized by treatment group and visit, and will be tested for difference in proportions separately at each specific timepoint. The analysis of these endpoints will be based on the mITT analysis population, and will mimic the analysis of primary effectiveness endpoint where only available data will be included, with the exception of presumed failures.

The secondary effectiveness endpoint of proportions of subjects considered dry (pad weight ≤ 4.0 grams) will be summarized by treatment group and visit. Difference between groups in the proportion of subjects dry will be presented, and tested for difference in proportions separately at each specific timepoint. The analysis of these endpoints will be based on the mITT analysis population, and will mimic the analysis of primary effectiveness endpoint where only available data will be included, with the exception of presumed failures. Further, the proportion of subjects dry based on the 1.3 gram cutoff instead of 4.0 grams will be assessed in a similar manner.

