12.1. General Considerations

All analyses will be performed by an independent statistician. Continuous variables will be summarized with means and standard deviations or as medians and interquartile ranges. Categorical variables will be summarized with the number and proportion of subjects in each category. Binary outcomes will be presented as proportions with corresponding 95% asymptotic confidence limits. Unless otherwise specified, two-sample t-test for independent groups or paired t-test will be used to test the means of continuous measures between groups, as appropriate. If assumptions of parametric tests are grossly violated, an equivalent non-parametric method may be sought. Fisher's exact test or binomial test will be employed to test categorical (including dichotomous) measures between groups.

The surgery date will be considered study day 0.

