12.7.4. Quality of Life

Change in Quality of life (QoL) scores (PGI-I, UDI-6, IIQ-7, SSQ-8) and VAS pain scores from baseline to follow-up will be summarized at each visit and for the Altis and Comparator group. Missing or incorrectly documented responses within a questionnaire will be handled according to the scoring algorithms. For each questionnaire, the Altis group will be compared to the Comparator group using a linear mixed model with repeated effects. An

unstructured correlation matrix will be specified to allow for maximal flexibility, but if convergence is not achieved, an autocorrelated or compound symmetry matrix will be used instead. An interaction term for time and treatment will also be assessed in the mixed model. Differences between the Altis group and the Comparator group will be assessed at each visit and overall.

For subjects with revision or resurgery within 36 months of the index surgery, QoL assessments following revision or resurgery will be evaluated.

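### Pad-weight change is tested for Altis superiority in a non-randomised cohort with no baseline pad-weight covariate named, so a baseline imbalance would favour whichever arm starts wetter

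*SAP*

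**What the plan says.** SAP 12.7.3 states that the pad-weight change since baseline "will be tested separately at each specific timepoint for superiority of the Altis group compared to the Comparator group", based on the mITT population, at 6, 12, 18, 24 and 36 months. It names no test for this, so the default in SAP 12.1 applies: "Unless otherwise specified, two-sample t-test for independent groups or paired t-test will be used to test the means of continuous measures between groups". That default has no covariates, and nor does the non-parametric alternative it allows.

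The same section adds a second analysis in which change in the Altis group "will be compared to the Comparator group using a linear mixed model with repeated effects". The only terms described are time, treatment and their interaction: "An interaction term for time and treatment will also be assessed in the mixed model". SAP 12.9 repeats this model as an exploratory analysis of the time effect.

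Four other provisions bear on the point:

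- SAP 12.7.3 also says: "As 24-hour pad weight and change from baseline in 24-hour pad weight are not study endpoints". Only available data are used, without imputation.
- SAP 12.6.3 builds a propensity score, but applies it to the two primary endpoints only. Its covariate list is open-ended and does not name baseline pad weight.
- SAP 12.4 compares baseline factors between arms, again from an open list that does not name pad weight. If they differ, it looks at the effect on success rates, not on continuous change.
- SAP 12.6.1 names baseline pad weight as a model variable, but only as a candidate for imputing the primary effectiveness endpoint.

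Protocol 7.7.1 planned only to assess differences in pad weight. The directional superiority test is in the SAP, which states that it prevails where the two documents differ.

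**The concern.** SAP 8.1 and 8.2 confirm that the study is neither randomised nor blinded, so similar baseline leakage in the two arms cannot be taken for granted. A change score in grams is a fair comparison only if equally effective devices would remove the same number of grams in both arms. Here they would not. A woman who starts at 20 g can lose at most 20 g, while one who starts at 100 g can lose five times as much. When most women improve by at least half, change largely reflects how wet they were before surgery.

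At stake is a pre-specified statement that Altis reduces leakage more than the comparator slings, made at up to five visits, when all or part of the difference could be a difference in starting severity. The same mechanism could hide a real Altis advantage if the Altis arm starts drier.

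**Working it through.** **1. Numbers per arm.** The plan states no figure for the pad-weight change test, so its own calculations supply only the arm sizes. The formula is n = (1.96 + 0.842)² × 2p(1−p) / margin², with (1.96 + 0.842)² = 7.849 from unrounded values.

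- Effectiveness (p = 0.75, margin 0.15): 7.849 × 0.375 / 0.0225 = 130.8, so 131. Then 131 / 0.8 = 163.75, so 164. Both match SAP 10.1.
- Safety (p = 0.10, margin 0.10): 7.849 × 0.18 / 0.01 = 141.3, so 142. Then 142 / 0.8 = 177.5, so 178. These match SAP 10.2 (142) and Protocol 7.9.3 (178).

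The planned 178 per arm with 20% loss leaves 0.8 × 178 = 142. The range 142 to 178 is used below, with 131 as a lower check.

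**2. Size of the bias.** Suppose both devices leave on average a fraction k of the baseline weight. Then:

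mean change = −(1 − k) × mean baseline

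Altis minus Comparator difference in change = −(1 − k) × baseline imbalance

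Example: 75% of women keep a fraction spread evenly over 0 to 0.5 (mean 0.25), and 25% keep 0.5 to 1.2 (mean 0.85). Then k = 0.75 × 0.25 + 0.25 × 0.85 = 0.40, and the spurious difference is 0.60 times the imbalance. For Altis 20% wetter this is 0.60 × 0.20 = 0.12 of the Comparator mean. Simulation gives 0.121 to 0.123.

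**3. How often identical devices give Altis superiority.** Assumed values, none of them in the documents: log-normal baseline, median 30 g, log-SD 1, 75% cured or nearly dry in both arms, no device difference. The implied mean is 30 × e^0.5 = 49.5 g and the CV is √(e − 1) = 1.31. An imbalance of 20% is therefore 9.9 g. The test is the t-test of change, counted when p < 0.05 in Altis's favour (nominal 2.5%).

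| Altis wetter by | 178 per arm | 142 per arm |
|---|---|---|
| 10% | 8.6-10% | 6.5-8% |
| 20% | about 21% | 16-19% |
| 30% | about 40% | 32-33% |

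The ranges come from separate runs that draw the follow-up weights somewhat differently, which the documents leave open. With 131 per arm the rates are 7.0%, 16.0% and 28.8%. With baseline as a covariate they are about 1-2.5% throughout.

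**4. Sensitivity.** These runs use the outcome law of step 2.

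- CV 1.0, Altis 10%, 20% or 30% wetter: 10%, 24% and 41% at 131 per arm; 12%, 29% and 53% at 178.
- Altis 20% wetter, 131 per arm: 36% with CV 0.7 and 17% with CV 1.3.
- No imbalance: 2.0-2.7%.
- Altis 20% drier: about 0%. The bias then runs against Altis.
- Baseline as covariate, CV 1.0, Altis 0% to 50% wetter: 2.1-3.1%.

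**5. Closed-form check.** Assume equal SDs before and after, pre/post correlation ρ, imbalance d in SD units, and no effect given baseline. The difference in change is (1 − ρ)d and its SD is √(2(1 − ρ)). For 131 per arm, d = 0.2, ρ = 0: SE = 1.414 × √(2/131) = 0.175, z = 0.2 / 0.175 = 1.145, and Φ(1.145 − 1.96) = 21%. For ρ = 0.5 the result is 13%.

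**6. Precision for the quality-of-life scores.** The residual variance with a baseline covariate, relative to a change score, is (1 − r²) / (2(1 − r)) = (1 + r) / 2. This is 0.65 at r = 0.3 and 0.75 at r = 0.5, a reduction of 35% or 25%. The correlations are assumed.

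**The case against.** The strongest reply is that little depends on this test. The SAP declares pad weight and its change not to be endpoints. Study success rests on the two primary objectives (SAP section 7, Trial Success Criteria). The explicit permission to claim Altis superiority is written for the primary and powered secondary endpoints, not here. The pad-weight endpoints are responder measures, a reduction of at least 50% and a weight of at most 4.0 g, and neither is an absolute change score. All of this stands, and it limits the severity.

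A reader might infer that Altis will appear superior. The documents do not support that. They report no baseline imbalance and nothing that predicts its direction. Even at an assumed 30% excess for Altis, about 60% of simulated trials with 178 per arm show no false superiority.

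A reader might also extend the bias to quality of life, because SAP 12.7.4 says that "the Altis group will be compared to the Comparator group using a linear mixed model with repeated effects". That section has change scores summarised, but does not say that change is the model outcome, and it specifies no superiority test. For those scales the documents support a gain in precision, not a finding of bias.

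It can be said that the SAP does not give a full list of model terms, and that the open lists in 12.4 and 12.6.3 could admit baseline pad weight. This is silence rather than an exclusion. But neither list reaches the analysis of continuous change, so the gap remains.

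Finally, adjustment is not a complete cure. It removes only measured differences, and a noisy baseline is under-corrected. With an assumed measurement log-SD of 0.5, Altis 30% wetter and 142 per arm, the adjusted test wrongly declared Altis worse in 6% of trials (nominal 2.5%). That residual bias runs the other way and is much smaller than the 32-33% without adjustment.

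**Conclusion.** The point holds as a conditional weakness in a supportive analysis. If the arms differ in baseline leakage, the tests and models of pad-weight change favour the wetter arm, and no other provision in the SAP corrects this. Under the stated assumptions, an imbalance of 10%, 20% or 30% towards Altis raises the false superiority rate from 2.5% to about 7-10%, 16-21% or 32-40% at 142 to 178 per arm. The direction follows from the zero bound and from similar proportional benefit. The size depends on a baseline spread and imbalance that the documents do not give. Study success is unaffected, and the responder endpoints do not rest on this analysis. Severity is low to moderate.

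**What to change.** - In SAP 12.7.3 and 12.9, add baseline pad weight as a covariate in the mixed models of continuous change.
- In SAP 12.7.3, replace the separate visit-wise t-tests with the visit contrasts from that model.
- In SAP 12.7.4, add the baseline score as a covariate for UDI-6, IIQ-7 and VAS pain, for precision. Leave out PGI-I and SSQ-8, which have no baseline assessment.
- State in the report that adjustment covers measured baseline differences only, and that error in the baseline pad test leaves some residual bias.

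The cost is a change of SAP wording. Protocol 5.1 already collects all the baseline values needed. Women without a baseline pad weight would drop out, but they already drop out of any change score.

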12.7.4. Quality of Life

Change in Quality of life (QoL) scores (PGI-I, UDI-6, IIQ-7, SSQ-8) and VAS pain scores from baseline to follow-up will be summarized at each visit and for the Altis and Comparator group. Missing or incorrectly documented responses within a questionnaire will be handled according to the scoring algorithms. For each questionnaire, the Altis group will be compared to the Comparator group using a linear mixed model with repeated effects. An

unstructured correlation matrix will be specified to allow for maximal flexibility, but if convergence is not achieved, an autocorrelated or compound symmetry matrix will be used instead. An interaction term for time and treatment will also be assessed in the mixed model. Differences between the Altis group and the Comparator group will be assessed at each visit and overall.

For subjects with revision or resurgery within 36 months of the index surgery, QoL assessments following revision or resurgery will be evaluated.

12.7.5. All Adverse Events

All adverse events will be summarized through 6, 12, 18, 24, and 36 months. The proportions of subjects with events will be reported as well as Kaplan-Meier event rates at the time points of interest. No imputation for missing data for the rates of adverse events is planned (with the exception of the secondary safety endpoints noted above). All safety summarized are based on mITT analysis population. Adverse events for subjects excluded from mITT analysis population (i.e., enrolled, but no implant was attempted) will be listed separately.

For subjects with revision or resurgery within 36 months of the index surgery, the rates of adverse events peri-procedural (within 30 days) following revision or resurgery will be assessed. Peri-operative adverse events will be summarized by relatedness separately for each treatment group.

Clinical Events Committee (CEC) will be used to adjudicate device and procedure related serious adverse events, and other events as deemed appropriate. The CEC adjudication will be used for all safety analyses. If an adverse event has not been reviewed by the CEC, the investigator's assessment will be used for all safety analyses.

Both the CEC and the investigator will assess the device and the procedure relatedness of the adverse event. The relatedness will be categorized as "definite", "probable", "possible", "not related" or "unknown". If the event is categorized as having a "definite", "probable" or "possible" relationship, it will be considered related for all safety analyses.

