10.4. Level of Significance and Power

All tests of significance will be performed at the two-sided 0.05 significance level (one-sided 0.025), unless otherwise specified. As both the primary effectiveness and safety objectives must be met for study success, no adjustment for multiplicity is required. Additionally, the powered secondary safety endpoints for (1) device and/or procedure related adverse events, and (2) revision or resurgery will be tested hierarchically in the order presented in the event the primary safety objective is met. Therefore, no adjustment for multiplicity is required.

10. Data Structure and Handling

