12.5. Study Endpoints

12.5.1. Primary Safety Endpoint

- Observed device and/or procedure-related serious adverse events through 36-months.

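### Events of 'unknown' relatedness are by implication left out of the two relatedness-based safety tests, which favours non-inferiority when Altis is truly worse

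*SAP*

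**What the plan says.** SAP 12.7.5 sets the grades: "The relatedness will be categorized as 'definite', 'probable', 'possible', 'not related' or 'unknown". Events in the first three grades count as related: "it will be considered related for all safety analyses". The section does not mention 'unknown' again. Device and procedure are graded separately: "Both the CEC and the investigator will assess the device and the procedure relatedness of the adverse event". The grade of the clinical events committee (CEC) is used where it has reviewed the event, and the investigator's grade otherwise.

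Two non-inferiority tests depend on these grades:

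- Primary safety, SAP 12.5.1 and 12.6.2: "Observed device and/or procedure-related serious adverse events through 36-months", with an absolute margin of 0.10.
- The first powered secondary safety endpoint, SAP 12.7.1: "The number and proportion of subjects experiencing any device- and/or procedure-related adverse event will be tabulated for each group", with an absolute margin of 0.15.

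Two other analyses do not depend on them:

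- Revision/resurgery, SAP 12.7.2: "The number and proportion of subjects experiencing any revision/resurgery will be tabulated for each group".
- The general summaries, SAP 12.7.5: "All adverse events will be summarized through 6, 12, 18, 24, and 36 months".

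Protocol 14.1.4 defines device-related and procedure-related events but has no 'unknown' grade. The SAP states that it prevails where the two documents differ.

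**The concern.** An event that was observed, but whose cause could not be determined, ends up on the favourable side of a test meant to rule out excess harm. Primary safety is one of the two objectives required for study success (SAP section 7, Trial Success Criteria), and it must be met before the hierarchical secondary safety tests (SAP 10.4).

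It is natural to think that a rule applied alike to both arms cancels out. On an absolute margin it does not. If the same fraction of related events is lost in each arm, a true difference shrinks by that fraction and the variance falls as well.

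The planned safeguards do not reach this case:

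- The best-case, worst-case, tipping-point and Kaplan-Meier analyses in SAP 12.6.2 and 12.7.1 address missing endpoint data and loss to follow-up. They do not address an observed event of undetermined cause.
- CEC review is assured only for device- and procedure-related serious events; other events go to it as deemed appropriate. A serious event that the investigator grades 'unknown' may therefore never be adjudicated.
- Study personnel are unblinded and treatment is not randomized, so equal use of 'unknown' in the two arms cannot be taken for granted.

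**Working it through.** **Inputs from the documents.** The level is "two-sided 0.05 significance level (one-sided 0.025") and power is 80%. Primary safety: 10% in each group, margin 0.10 (SAP 10.2, 12.6.2). Related adverse events: 20% in each group, margin 0.15 (SAP 10.3, 12.7.1). Planned size: 178 per arm (SAP section 8).

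**Input not in the documents.** u is the share of truly related endpoint subjects lost because relatedness is 'unknown'. It is assumed to be between 1% and 20%.

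**The plan's own figures.** n = (1.960 + 0.842)² × 2p(1−p) / margin².

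- Primary safety: 7.849 × 0.18 / 0.01 = 141.3, so 142 per group, as in SAP 10.2. Then 142 / 0.80 = 177.5, so 178, as in Protocol 7.9.3.
- Related adverse events: 7.849 × 0.32 / 0.0225 = 111.6, so 112 per group, as in SAP 10.3.

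The stated sizes reproduce, so the same normal approximation is used below.

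**Altis truly worse by the margin.** Each true rate is multiplied by (1−u). With d the resulting difference (Altis minus Comparator),

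P(non-inferiority) = Φ((margin − d)/SE − 1.960), where SE² = [pC(1−pC) + pT(1−pT)]/178.

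Primary safety with u = 10%: the rates become 0.09 and 0.18, so d = 0.09. SE = √((0.0819 + 0.1476)/178) = 0.0359. The argument is 0.01/0.0359 − 1.960 = −1.68, and the error is 0.046.

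| u, equal in both arms | Primary safety, d (true 10% vs 20%) | Primary safety, error | Related AEs, error (true 20% vs 35%) |
|---|---|---|---|
| 0 | 0.100 | 0.025 | 0.025 |
| 1% | 0.099 | 0.027 | 0.027 |
| 5% | 0.095 | 0.034 | 0.036 |
| 10% | 0.090 | 0.046 | 0.052 |
| 20% | 0.080 | 0.085 | 0.102 |

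Exact binomial enumeration for primary safety gives slightly higher values: 0.027, 0.029, 0.037, 0.050 and 0.092.

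**Unequal use.** If 10% of related endpoint subjects are lost in Altis only, the rates are 0.10 and 0.18 and the error is 0.079 (exact 0.084).

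**Equal true rates of 10%.** d stays 0 and only the SE falls. At u = 0, 0.10/0.0318 − 1.960 = 1.18, so the chance of passing is 0.882. At u = 10%, 0.10/0.0303 − 1.960 = 1.34, so it is 0.909.

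**Effect of counting 'unknown' as related.** Let b be the share of subjects without a related serious event who would be wrongly counted; each rate p becomes p + (1−p)b. With no related event lost:

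| b | Error (true 10% vs 20%) | Chance of passing (true 10% vs 10%) |
|---|---|---|
| 0 | 0.025 | 0.882 |
| 1% | 0.027 | 0.857 |
| 2% | 0.028 | 0.833 |
| 5% | 0.033 | 0.764 |
| 10% | 0.041 | 0.672 |

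**The case against.** Four objections deserve weight.

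1. **The SAP does not say that 'unknown' means not related.** A reader might infer an explicit rule to that effect, but the text is silent. Exclusion follows only because no sentence brings these events in. This stands, and the point is worded accordingly.

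2. **A reader might infer that every safety analysis is affected, or that the difference is always biased.** Neither is supported. Revision/resurgery and the summaries of all adverse events need no relatedness grade. With equal true rates the expected difference is unchanged, and if Altis were truly safer, equal loss would understate its advantage.

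3. **The share may be small.** An 'unknown' event changes a subject's status only if it is truly related, does not reach 'possible' on the other axis, and is the subject's only qualifying event. 'Possible' already counts as related, which absorbs ordinary doubt, and an independent committee adjudicates related serious events. At 1% the error is only 0.027. This stands as a limit on size, not on direction. The Altis-only figure shows what unequal coding would do; the documents give no evidence that such coding occurs.

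4. **Counting 'unknown' as related also misclassifies.** It brings in unrelated events and dilutes the difference too. This is correct, but the scales differ. A loss of u = 10% removes 2% of subjects in an arm with a 20% rate and 1% in an arm with a 10% rate, and the error is 0.046. Wrongly adding 1–2% of subjects without a related event gives 0.027–0.028. The dilution does not cancel the gain. The loss of power is real and must be stated.

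**Conclusion.** The point holds for two tests, primary safety and the powered related-adverse-event endpoint. As the SAP is written, observed events of unknown cause drop out of both. This is anti-conservative when Altis is truly worse, even with equal use of the grade in both arms.

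The size rests on an assumed share. Over 1% to 20%, the one-sided error of the primary safety test runs from 0.027 to 0.085 against a nominal 0.025, at true rates of 10% and 20% with 178 per arm. The documents give no frequency for 'unknown', so these figures are scenarios, not estimates. The calculation also assumes equal loss in both arms and the normal approximation that the plan itself uses. A reader might infer that the trial's safety conclusion is unsound; the documents do not support that. They show a gap in the counting rule that is worth closing and cheap to close.

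**What to change.** In SAP 12.7.5, state how 'unknown' is handled. For the primary safety endpoint and the powered related-adverse-event endpoint, count an event as related if it is graded 'unknown' on device or procedure and is not already at least 'possible' on the other axis. Report the analysis with these events as not related as a sensitivity analysis.

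If the sponsor prefers to keep the present counting as the main analysis, the minimum is to state it explicitly, pre-specify the analysis that counts 'unknown' as related, and require the non-inferiority conclusion to be reported under both rules.

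The cost is one sentence and one extra table, with no new data. Observed related-event rates rise slightly in both arms. At equal true rates of 10%, the chance of passing the primary safety test falls from 0.882 to about 0.86 or 0.83 if 1% or 2% of subjects without a related serious event are added. It falls further if the grade is used more often.
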